7.1 DEMOGRAPHIC AND OTHER BASELINE CHARACTERISTICS

Details of the analysis of demographic and other baseline characteristics can be found in [Section 7.6](#).

7.2 CONCOMITANT DISEASES AND MEDICATION

Details of the analysis of concomitant diseases, medical history and concomitant medication at the time of baseline visit (including PGP-inhibitor/ PGP-inducer) can be found in Section 7.6.

For antihypertensive, heart failure and antiarrhythmic co-therapies and for intermittent NSAIDs use, proportion of patients with co-medication will be summarized by visit and antithrombotic treatment prescribed at baseline based on all eligible patients and the full observation time (irrespective of treatment change).

Patients with/without intervention including type of intervention for cardioversion, AF-ablation, pacemaker implantation and major surgery and minor surgery) during Dabigatran period will be characterized. The analysis might be considered for other treatment groups.

7.3 TREATMENT ADHERENCE

“Adherence” in the context of this study encompasses treatment compliance and persistence. Analysis of treatment compliance and persistence is defined as further analysis. Details regarding the further analyses can be found in [Section 7.7](#).

7.4 METHODS ADDRESSING BIAS

In order to assess the effects of lost to follow-up patients, percentages of dropouts and reason for loss to follow-up will be summarized in patients with a pre-planned follow up (all patients in Phase III). In addition, baseline characteristics of patients (including treatment) will be compared over all treatment groups (full cohort) between:

- Patients who were lost to follow-up
- patients with a complete follow-up
- patients who discontinue early for other reasons,

Only categories with at least 100 patients will be considered for the comparison. If the number of patients lost to follow-up is below 100, this group will not be characterized separately but pooled with patients discontinued early for other reasons. In addition, see analyses described in Sections 7.6, and 7.7.

7.5 METHODS ADDRESSING CONFOUNDING / EFFECT MEASURE MODIFICATION

See analyses described in Sections 7.6, 7.7.

7.6 MAIN ANALYSES

Analyses for the main outcome events are mainly defined for patients in the restricted patient set and, in some occasions for patients in the eligible patient set who took at least once the treatment and patients in the matched patient set. All those analyses in this section for the main outcome events that are defined on the restricted and eligible patient sets will be repeated as well for the EU 1160.136 study if not stated otherwise.

If not stated otherwise, the main analyses of longitudinal outcomes will be as-treated (only the first treatment period is included), censoring patients after the initial treatment regimen episode stop (see [Section 6.8](#)).

Patient characteristics influencing choice of antithrombotic treatment at baseline

Demographics and baseline characteristics (including stroke/bleeding risk scores, and pre-treatment of OAC) will be summarized descriptively for all eligible patients by antithrombotic treatment choice for long-term treatment at the baseline visit. This will be repeated overall and on a regional level for patients included in the restricted patient set, i.e. for Dabigatran and VKA patients only. For the matched cohort, i.e. for Dabigatran and VKA patients a condensed set of baseline variables will be summarized. In case additional restricted and matched patient sets would be derived for other treatment groups, the same analyses could be performed.

Baseline data might be further analyzed in post-hoc tables showing the treatment distributions (with different treatment group categorizations) within specific subgroups.

Important outcome events – Incidence rates

For the main treatment groups including the total group as defined in [Table 6.1: 1](#) and for all important outcome events including the two composite outcomes incidence rates with 95%-CIs, cumulative risks, and KM curves will be calculated on the eligible patient set on the first treatment period only. Only patients from the eligible patient set that took the prescribed treatment at least once are considered. Patients who discontinue initial antithrombotic treatment for stroke prevention permanently will be censored at date of last drug intake + 3 days (for dabigatran and non VKA treatments) and +6 days (for VKA treatment or combinations of VKA with other antithrombotic treatments) or at first intake of other relevant chronic antithrombotic treatment for stroke prevention, whatever comes first (unless the event occurred prior to the time of censoring). A patient is considered to have permanently stopped initial antithrombotic treatment for stroke prevention, if other relevant chronic antithrombotic treatment is initiated for stroke prevention or otherwise dependent on the duration of treatment interruption.

The main analysis of overall incidence rates with 95% confidence intervals, cumulative risks and KM curves will be repeated for at least the following subgroups, acknowledging the limited precision given the sample size: region (1160.129 only), chronic antiplatelet treatment (1160.136 only), antithrombotic treatment, age, gender, CHADS2, CHA2DS2-VASc and HAS-BLED risk scores. A graphical (forest-plot-like) display will additionally be prepared to

summarize the subgroup results per outcome on the eligible patient set for the first treatment period only. Additional subgroup analyses might be conducted as needed.

For all important outcome events (including composite outcomes) for patients initiating VKA at baseline, and patients initiating Dabigatran at baseline, incidence rates, cumulative risks with 95%-confidence intervals will be calculated by treatment, and for a graphical comparison Kaplan Meier curves will be plotted. These statistics will be calculated on the restricted and the matched patient sets and only the first treatment period is taken into account, i.e. patients who never took the prescribed treatment will not be included.

For the matched and the restricted patient sets as a sensitivity analysis, the calculation of incidence rates and cumulative risks will be performed without censoring at permanent discontinuation of initial antithrombotic treatment for stroke prevention (intention to treat (ITT) approach). KM curves will be plotted.

Dependent on the number of patients receiving different antithrombotic treatment for stroke prevention and dependent on comparability of important baseline characteristics, restricted and matched patient sets may be considered for other pairwise treatment regimes. In this case, the analyses defined here for dabigatran and VKA could be performed for other treatment groups.

Further outcome events

For the further outcome events such as transient ischemic attack (TIA) or stroke (instead of TIA alone), ischemic stroke and hemorrhagic stroke incidence rates, KM estimates and KM curves will be calculated on the eligible patient sets for all main treatment groups (see [Table 6.1: 1](#)). For patients initiating VKA at baseline and patients initiating Dabigatran at baseline, above analyses will be performed on the restricted and matched patient sets on the first treatment period only.

Dependent on the number of patients receiving different antithrombotic treatment for stroke prevention and dependent on comparability of important baseline characteristics, for further outcomes mentioned above, the incidence rates, KM estimates and KM curves might be calculated on the restricted and matched patient sets for other pair-wise treatment regimes, similar to the analysis as outlined for Dabigatran and VKA.

Technical specifications

Incidence rates per 100 patient years with 95%-confidence intervals for important outcome events (single and composite outcome) will be calculated the following way. In addition these analyses will be done stratified by chronic antiplatelet treatment at baseline. Recurrent events will be disregarded for calculation of incidence rates. Incidence rate λ is defined as

$$\text{Incidence rate } \lambda \left[\frac{1}{100} \text{ pt.yrs} \right] : \\ = 100 * \frac{\text{number of patients with event}}{\frac{1}{365.25} * \sum_{\text{patients}} \text{person time at risk (event)} [\text{days}]}$$

where the denominator is the patient years under risk. The 2-sided 95% CI of λ will be calculated based on the Poisson distribution and its relation with the Chi-square distribution according to the following formula [7]:

$$[\lambda_{\text{lower}}, \lambda_{\text{upper}}] = [\{0.5 \chi^2(\alpha/2; 2x)\}/n, \{0.5 \chi^2(1-\alpha/2; 2x+2)\}/n],$$

where $\chi^2(\gamma, r)$ is the 100 γ th percentile of a chi-square distribution with r degrees of freedom, n is the patient years under risk for the event, x is the number of patients with event, and α for (1- α) % 2-sided CIs.

Cumulative risk is defined as cumulative proportion of patients with event and will be calculated as the Kaplan-Meier estimate for failure. The Kaplan-Meier curve will be plotted. The proportion of patients with event, as well as the proportion of censored patients falling into specified intervals and the Kaplan-Meier estimate for failure will be computed for the following categories:

- ≤ 3 months
- $3 < \text{and } \leq 6$ months
- $6 < \text{and } \leq 12$ months
- $12 < \text{and } \leq 18$ months
- $18 < \text{and } \leq 24$ months
- $24 < \text{and } \leq 30$ months
- > 30 months

In the following if not stated otherwise for all analyses only patients from the restricted patient set are considered. Furthermore only the first treatment period is included (i.e. as-treated analysis) if not mentioned otherwise (like e.g. for ITT analyses).

- 1) Main analysis of composite outcome (Stroke, systemic embolism, myocardial infarction, life-threatening bleeding events and vascular death)

Acknowledging the limited precision given the sample size and the potential limitations, for the main comparison of the two treatment groups, Dabigatran and VKA, with regards to the composite outcome a multivariable Cox regression model (according to the 1160.129 and 1160.136 protocols) will be performed if those patient groups are determined to be comparable in terms of the PS analysis. The multivariable Cox regression model will include the following variables as core variables: treatment, age (<65 , $65-75$, >75), gender and the following main stroke and bleeding risk factors: prior bleed, previous stroke/TIA, previous myocardial infarction, abnormal kidney function and concomitant antiplatelets use. The following further covariates will be investigated within a model selection procedure: (sub)region, congestive heart failure, left ventricular

hypertrophy, systemic embolism, complex aortic plaque, hypertension, diabetes mellitus, PAD, CrCl, NSAID use type of AF, hepatic disease, alcohol abuse, any drug (HAS-BLED), previous OAC use (within 3 months), smoking status, and concomitant medication like antipsychotics.

The correlation of covariates will be assessed and in case of a high correlation between two or more covariates the exclusion of at least one covariate might need to be discussed. Exclusion of covariates with high proportion of missing values might be considered.

The further covariates selection procedure will start with the baseline model including all core variables and will add only one of the further variables at a time. Only the variable which has the largest effect on the treatment estimate will be included in the next step model and only if the treatment effect estimate (hazard ratio) is relatively changed by more than 10% in comparison to the model with the core variables only. This step is repeated on the new model until none of the other variables change the treatment effect estimate by more than 10% in comparison to the resulting model from the previous step. To account for model overfitting, another restriction will be the number of events in comparison to the number of degrees of freedom required to represent all of the variables in the model. For example, a three-level categorical variable would require two degrees of freedom. The number of degrees of freedom for all variables*10 shall not exceed the number of events reported for the composite outcome. For example if 200 events are reported for an outcome, than the number of degrees of freedom summing up over all covariates included in the model is not allowed to exceed 20. If so the last covariate resulting from the last step of the model selection procedure process which was about to be included in the main model needs to be excluded from the final model and the selection process is stopped and the previous model resulting from the previous step is checked in the same way. Generally the selection procedure will be stopped as soon as the number of degrees of freedom for all covariates in the model multiplied by 10 exceeds the number of events.

Patients who discontinue initial antithrombotic treatment for stroke prevention permanently will be censored at date of last drug intake + 3 days (for dabigatran and non-VKA treatments) and +6 days (for VKA treatment or combinations of VKA with other antithrombotic treatments) or at first intake of other relevant chronic antithrombotic treatment for stroke prevention, whichever comes first (unless the event occurred prior to the time of censoring). A patient is considered to have permanently stopped initial antithrombotic treatment for stroke prevention, if another relevant chronic antithrombotic treatment is initiated for stroke prevention (switch) or depending on the duration of treatment interruption (see [Section 6.1.2](#)). Treatment effects and subgroup variable effects will be reported.

Multiple imputation methods (e.g. the fully conditional specification method) will be used to impute both continuous and categorical variables appropriately with arbitrary missing patterns. Each single step of the variable selection procedure above should be based on the combined estimates of the parameter estimates from all the models using the multiple imputed datasets.

- 2) Sensitivity analyses for composite outcome (Stroke, systemic embolism, myocardial infarction, life-threatening bleeding events and vascular death)

For 1160.136, only the sensitivity analyses on the ITT approach (d) and the sensitivity analyses on other multivariate models (f) will be performed.

- a. **The primary sensitivity analysis** for the comparison between dabigatran and VKA treatment groups in terms of the composite outcome of stroke, SEE, vascular death, MI, life-threatening bleeds will be a **stratified analysis based on propensity scores and stratified by region**. For the stratification process the PS will be categorized by e.g. deciles or quintiles based on the smaller treatment group and depending on the number of patients per region. A Cox model with treatment as the only independent variable will be used. The stratified results will be combined to end up with one final effect estimate.
- b. The main analysis will be repeated using a different variable selection procedure resulting in a potentially different model. Here the variable selection will be based on a forward likelihood ratio selection procedure based on p-values (e.g. cut-off $p>0.2$). The core variables will be fixed and the selection procedure will only be performed for the set of further covariates listed above. Again, to account for model overfitting, another restriction will be the number of events in comparison to the overall number of degrees of freedom for all covariates included in the model. The number of degrees of freedom* 10 shall not exceed the number of events reported for the composite outcome.
- c. One further sensitivity analysis for the composite outcome will be a PS matched pair analysis (1:1 greedy nearest neighbour matching using calipers equal to, e.g. 0.2 standard deviations of the logit of the estimated propensity score, matching will be performed within region). The Cox regression model to analyse the matched data with regards to the composite outcome will be performed with only treatment as the independent variable but taking into account the dependencies within the matched pairs by including a frailty parameter into the Cox model. The balance in measured covariates will be assessed using standardized mean differences. A covariate with a difference $> 10\%$ (in absolute value) will be considered unbalanced between the two treatment groups. For these unbalanced covariates, another Cox model will be optionally performed including treatment and the residually imbalanced variables. Furthermore baseline characteristics of the matched cohort after matching will be provided.
- d. In addition, Cox regression analysis (based on the main analysis model) will be performed **without censoring at permanent discontinuation of initial antithrombotic treatment for stroke prevention (intention to treat (ITT) approach)**.
- e. Regarding the main model for the composite outcome: **An additional sensitivity analysis will be conducted to assess the effect of telephone visits on outcome event reporting rates**. For this analysis, patients will be censored if they miss more than 1

consecutive physical visit (censoring date will be the last physical visit prior to the consecutive telephone/missed visits). In addition, patients who had their last study visit as telephone visit will be censored at their last physical visit. An event will only be counted for this analysis if it occurs during the initial treatment regimen episode of the antithrombotic therapy selected at baseline (as defined in [Section 6.1.2](#)) and prior to the time point of censoring. Start dates for calculation of time to event and time to censoring are defined as for the main analysis.

- f. In order to explore which factors potentially modify the effect of dabigatran vs. VKA in terms of occurrence of the composite outcome, additional interaction terms (treatment*(factor potentially impacting safety and effectiveness)) might be included in multivariable regression models similar to the final main model. Factors to be explored include stroke risk factors as those might impact safety and effectiveness of dabigatran. Forest plots will be used to graphically summarize the treatment effects in the different subgroups.
- g. Another sensitivity analysis on the main model might be performed using treatment-naïve patients only, i.e. patients without any OAC treatment within the last 3 months prior to the baseline visit.
- h. An imputation method similar to Phase II for the multivariable regression analyses might be performed on the main model. Missing information on risk factor variables (binary variables) with a frequency (prevalence) below 50% in patients with data will be treated as absence of risk factor. Missing information on intake of co-medication at baseline will be considered as no intake of the co-medication. The risk scores (derived variables e.g. Has-Bled score) will be calculated from the (possibly imputed) components. For missing variables that have not been described as risk factors for stroke or major bleeding in the literature nor have a known impact on PK/PD of the treatments analyzed, a value will be randomly assigned based on the distribution of patients with values.
- i. To explore the impact of the primary imputation approach for unknown cause of death, the following two alternative approaches will be considered: (1) Unknown cause of death will be imputed as a vascular cause; (2) Unknown cause of death will be imputed as a non-vascular cause.
- j. The main analysis might be repeated using a different composite outcome definition: replacing vascular death with all cause death in the composite outcome
- k. One more sensitivity analysis might be performed by repeating the main analysis using different definitions of washout and gap for treatment discontinuation

3) Analyses of other outcome events

The following Cox models will only be performed if enough events are reported such that the number of events is roughly proportional to the number of degrees of freedom for all the covariates included in the Cox model. If for other kind of outcome events not listed below

enough events are reported a similar kind of analysis might be performed. The same model selection procedure approach as used for the composite outcome will be used. For all models below the following rule of thumb applies as in the main model used for the composite outcome. The number of degrees of freedom for all covariates in the model * 10 roughly shall not exceed the number of events reported for the composite outcome. The PS matched pair analysis on the specific outcome event might be performed for all outcomes. Additional sensitivity analyses for the single outcome events similar to the ones described for the composite outcome under 2) a),c),f) will be performed if the number of events reported is large enough and additional above mentioned sensitivity analysis will be considered.

- *Composite vascular outcome*

Using the same methods as described above for the composite outcome under 1), VKA and Dabigatran treated patients will be compared in terms of the vascular composite outcome using the same approach for the main analysis and the same sensitivity analyses a), c), f), and i) as outlined for the composite outcome above. Additional above mentioned sensitivity analysis might be considered.

- *Stroke/SEE (optional)*

For stroke/SEE events the multivariable Cox model will include the following variables as core variables as used for the composite outcome: treatment, age (<65, 65-<75, >=75), gender and stroke and bleeding risk factors: prior bleed, previous stroke/TIA, previous myocardial infarction, abnormal kidney function, and concomitant antiplatelet use.

Further covariates will be selected within the model selection procedure: (sub)region, congestive heart failure, left ventricular hypertrophy, systemic embolism, complex aortic plaque, hypertension, diabetes mellitus, PAD, CrCl, NSAID use (including missing/unknown as a separate category), type of AF, complex aortic plaque, hepatic disease, alcohol abuse, any drug (HAS-BLED), smoking status, concomitant medication like antipsychotics, previous OAC use (within 3 months).

A similar model might be run on stroke events alone if the number of events reported is large enough.

- *Major Bleeding*

For the major bleeding outcome event the multivariable Cox model will include the following variables as core variables: treatment, age (<65, 65-<75, >=75), gender and the following bleeding risk factors: prior bleed, abnormal kidney function, any drug-HAS-BLED, and concomitant antiplatelet use. Further covariates will be selected within a model selection procedure: (sub)region, congestive heart failure, previous stroke/TIA, previous myocardial infarction, left ventricular hypertrophy, systemic embolism, complex aortic plaque, hypertension, diabetes mellitus, PAD, CrCl, NSAID use (including missing/unknown as a separate category), type of AF, complex aortic plaque, hepatic disease, alcohol

abuse, smoking status, concomitant medication like antipsychotics, previous OAC use (within 3 months).

- *All Cause Death (optional)*

For death events the multivariable Cox model will include the following variables as core variables like used for the composite outcome: treatment, age (<65, 65-<75, >=75), gender and the following main stroke and bleeding risk factors: prior bleed, previous stroke/TIA, previous myocardial infarction, abnormal kidney function and concomitant antiplatelets use. Further covariates will be selected within a model selection procedure: (sub)region, congestive heart failure, left ventricular hypertrophy, systemic embolism, complex aortic plaque, hypertension, diabetes mellitus, PAD, CrCl, NSAID use (including missing/unknown as a separate category), type of AF, complex aortic plaque, hepatic disease, alcohol abuse, any drug (HAS-BLED), smoking status, concomitant medication like antipsychotics, previous OAC use (within 3 months).

- *Myocardial Infarction (optional)*

For MI events the multivariable Cox model will include the following variables as core variables: treatment, age (<65, 65-<75, >=75), gender and the following MI risk factors (hypertension, diabetes mellitus, previous myocardial infarction) and concomitant antiplatelet use. Further covariates will be selected within a model selection procedure: (sub)region, left ventricular hypertrophy, systemic embolism, complex aortic plaque, congestive heart failure, PAD, CrCl, NSAID use (including missing/unknown as a separate category), type of AF, complex aortic plaque, hepatic disease, alcohol abuse, any drug (HAS-BLED), smoking status, concomitant medication like antipsychotics, previous OAC use (within 3 months).

If sample size allows, comparisons of other outcomes may be considered for either 1160.129 or 1160.136, if needed.

Dependent on the number of patients receiving different antithrombotic treatment for stroke prevention and dependent on comparability of important baseline characteristics, other pairwise comparisons of the treatment regimes regarding outcome events might be performed similar to the analysis as outlined for Dabigatran and VKA if the total number of events does allow for a meaningful comparison.

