For Phase II a total sample size of 5,000 patients allows an estimation of a population attribute with a precision of less than 2.8% (i.e. width of 95% CI).

For subgroups which consist of at least 500 patients; this allows an estimation of a population attribute within the subgroup with a precision of approximately 8.9% (i.e. width of 95% CI).

For Phase III a total sample size of 10,000 patients allows an estimation of a population attribute with a precision of less than 2.0% (i.e. width of 95% CI).

Estimates for incidence rates (Phase II-III):

Estimates and confidence intervals for incidence rates (interpreted on a descriptive level) will be computed. For Phase II it is estimated to recruit approximately 2,500 patients from EU/EEA member states in the dabigatran treatment cohort whom are followed up for up to 2 years. Assuming a total treatment discontinuation and lost to follow-up rate of 25% per year a

Proprietary confidential information.

© 2014 Boehringer Ingelheim International GmbH or one or more of its affiliated companies. All rights reserved.

This document may not - in full or in part - be passed on, reproduced, published or otherwise used without prior written permission.

total of approximately 3,802 patient-years in patients from EU/EEA member states starting dabigatran will be observed.

When observing 3,802 dabigatran patient years, we will observe at least one patient with an event (ADR, MBE, stroke/SEE, etc), if the underlying incidence rate for this event is 0.079 occurrences per 100 patient years or above with a power of 95%. If we do not observe any event within the 3,802 patient years, it can be excluded with 95% confidence that the underlying true event rate is above 0.079 per 100 patient years in the population.

Based on the recent RE-LY trial (warfarin, dabigatran), it is expected that the incidence rates for stroke/SEE and MBE will be in a range of 1 to 3 per 100 patient years in the total population. The width of the two-sided 95% confidence interval of the population depends on the obtained estimate from the sample of 3,802 patient years; the following table illustrates this relationship:

Table 7.6: 2 95% Confidence intervals based on different scenarios for observed event rates (based on 3,802 patient years)

| Observed event rate per 100 patient years | Lower 95% CI for event rate per 100 patient years | Upper 95% CI for event rate per 100 patient years |
|---|---|---|
| 1 | 0.70773 | 1.372465 |

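### The SAP's confidence-interval formula for outcome incidence rates omits the factor 100 in the rate it accompanies, so the limits as written are 100-fold too low

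*SAP*

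**What the plan says.** The technical specifications in SAP section 7.6 open with the scope: "Incidence rates per 100 patient years with 95%-confidence intervals for important outcome events (single and composite outcome) will be calculated the following way". The rate λ is then displayed as 100 times the number of patients with event, divided by the summed person-days at risk over 365.25. The text adds, "where the denominator is the patient years under risk".

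The interval is declared to be for this same λ: "The 2-sided 95% CI of λ will be calculated based on the Poisson distribution and its relation with the Chi-square distribution". The limits carry the symbols λ_lower and λ_upper. They equal 0.5·χ²(α/2; 2x) and 0.5·χ²(1−α/2; 2x+2), each divided by n. The symbols are defined in words: "n is the patient years under risk for the event, x is the number of patients with event". No factor of 100 appears in the limits or in the definition of n. The confidence level is written as (1−α) followed by a percent sign.

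Protocol section 7.6 uses chi-square quantiles from the same textbook. Its Table 7.6: 2 is titled "Confidence intervals based on different scenarios for observed event rates (based on 3,802 patient years"), and both the observed rates and the limits are labelled per 100 patient-years.

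**The concern.** The estimate and its limits share a symbol but not a unit: λ is per 100 patient-years, while λ_lower and λ_upper are per patient-year. A program written literally from the SAP would print an interval that cannot belong to the rate beside it.

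This is the only symbolic interval formula in the two documents for these rates. It serves the important outcome events and both composites, by treatment group, on the eligible, restricted and matched patient sets, and it also serves the subgroup displays and the intention-to-treat version of the rates. SAP section 3 says that the document exists to give procedures for carrying out the analyses. A programmer or independent validator should therefore be able to use the formula as it stands. Someone who corrects it silently obtains the right interval but departs from the written plan without a record.

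**Working it through.** **Inputs**
- λ = 100·x/n, with x patients with event and n patient-years (SAP 7.6).
- Limits as written: 0.5·χ²(α/2; 2x)/n and 0.5·χ²(1−α/2; 2x+2)/n, with n in patient-years (SAP 7.6).
- Two-sided 95%, so α = 0.05 (SAP 7.6).
- n = 3,802 patient-years, with rates of 1, 2 and 3 per 100 patient-years (Protocol 7.6, Table 7.6: 2). This n is the protocol's Phase II planning figure. It serves here only as a worked example, because the scale error does not depend on n.

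**Step 1. Reproduce the protocol's table.** The table's rates imply x = rate × 3,802/100, which is 38.02, 76.04 and 114.06. The limits are computed once as written and once multiplied by 100.

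| λ per 100 PY | x | SAP formula as written | Multiplied by 100 | Protocol Table 7.6: 2 |
|---|---|---|---|---|
| 1 | 38.02 | 0.00708 to 0.01372 | 0.70773 to 1.372465 | 0.70773 to 1.372465 |
| 2 | 76.04 | 0.01576 to 0.02503 | 1.575877 to 2.503151 | 1.575877 to 2.503151 |
| 3 | 114.06 | 0.02475 to 0.03604 | 2.474761 to 3.603743 | 2.474761 to 3.603743 |

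All three rows agree to the printed digits after multiplication by 100, and none agrees without it. With a whole number of events, x = 38, the rescaled limits are 0.7073 to 1.3719. These match the protocol's worked example (0.71 to 1.37) at two decimals. The table's extra digits require x = 38.02.

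**Step 2. Does the literal interval contain its estimate when x ≥ 1?** Multiply everything by n, so that n cancels. The estimate becomes 100·x and the upper limit becomes 0.5·χ²(0.975; 2x+2).
- x = 1: 0.0014655 × 3,802 = 5.57, against 100.
- x = 5: 0.0030690 × 3,802 = 11.67, against 500.
- x = 38: 0.0137186 × 3,802 = 52.16, against 3,800.

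The ratio of the upper limit to x is 5.57, then 11.67/5 = 2.33, then 52.16/38 = 1.37. It falls as x grows and would have to reach 100 for the interval to contain λ. The literal interval therefore excludes its estimate for any x ≥ 1 and any n.

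**Step 3. Zero events.** λ = 0, and the upper limit as written at n = 3,802 is 0.00097. The interval from 0 to 0.00097 contains 0, but the upper limit on the rate's own scale is 100 × 0.00097 = 0.097 per 100 patient-years. The lower-limit formula calls for a chi-square quantile with 0 degrees of freedom, which is undefined. The SAP states no convention for that case.

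**Step 4. Confidence level.** At α = 0.05, (1−α)% reads literally as 0.95%, whereas 100(1−α)% gives 95%.

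**The case against.** The strongest reply is that this is a notational slip that would mislead nobody. The section says that the rates are per 100 patient-years, λ is labelled with that unit, and the interval is said to be for λ. The SAP builds on protocol section 7 and assumes that the reader knows it. That section prints correctly scaled limits for three rates and a worked example. An interval of about 0.007 to 0.014 beside an estimate of 1.00 would be noticed in any table or forest-type plot. No decision rests on these limits, since protocol section 7.2 foresees no confirmatory testing.

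Most of this stands. It bears on how likely the error is to reach a report, not on whether the formula is right. The missing factor cannot be put down to text extraction, because n is also defined in words as patient-years.

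A reader might also infer more than the documents support:
- That every literal interval excludes its estimate. The zero-event interval does not.
- That all incidence rates in the study are affected. The specification covers important outcome events, single and composite. Rates for serious adverse events and adverse drug reactions follow the sponsor's separate standards (SAP 7.9.1.4).
- That the interval method is wrong. The exact Poisson method is appropriate and reproduces the protocol's table once scaled.
- That the treatment comparison is compromised. Dabigatran and VKA are compared by Cox models, which do not use this formula.

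**Conclusion.** The formula is wrong as written. For important outcome events, both limits are too low by a factor of exactly 100, whatever the event count or follow-up. With at least one event the interval excludes its own estimate; with none, only the upper limit is affected.

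The conclusion rests on reading λ, n and the limits as the SAP defines them. The statement of what was intended rests on protocol Table 7.6: 2, which is reproduced in all three rows only after rescaling. No figure printed in either document is wrong because of this slip, and the documents give no ground for inferring that reported intervals would be wrong, since a literal program's output would be conspicuous. It is a minor point: a correction to a working formula with no bearing on design, data or method.

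**What to change.** In the technical specifications of SAP section 7.6:
- Multiply both limits by 100: λ_lower = 100·0.5·χ²(α/2; 2x)/n and λ_upper = 100·0.5·χ²(1−α/2; 2x+2)/n. Alternatively, keep the formula and define n as patient-years at risk divided by 100.
- State that λ_lower = 0 when x = 0.
- Write the confidence level as 100(1−α)%.

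Protocol Table 7.6: 2 can serve as the validation case for the program, using x = 38.02, 76.04 and 114.06 with n = 3,802.

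The cost is one corrected formula and a line in the SAP history table. No analysis choice, data item or sample-size figure changes.
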